Fifty-one participants with PD will be recruited with the following inclusion criteria for study part III: 1) Aged 40 to 70, 2) Diagnosed with idiopathic Parkinson's disease by a neurologist 3) Hoehn & Yahr Scale Stage II to III with stable medications usage 4) ability to walk independently with or without walking aids for 10 metres. The exclusion criteria are as follow: 1) severe comorbidity that may interfere with their ability to participate in the study (e.g. chronic obstructive airway disease, angina, congestive cardiac failure, and significant renal or liver disease, malignancy) 2) significant orthopaedic or rheumatological conditions or disorders of peripheral nervous system that may interfere with mobility or balance performance 3) Female subjects who are pregnant 4) Neurological disease other than PD 5) a score of less than 23 on the Mini-Mental State Examination 6) any auditory or visual impairment 7) History of neurosurgery 8) contraindication to TMS including personal or family history of seizure disorder, metal in the head, implants of medical devices such as cardiac pacemakers or medical pumps (Appendix 1). 9) Subjects with irrepressible tremor and/dyskinesia. Informed consent in accordance with the Declaration of Helsinki will be obtained from all participants and data collection will only be carried out after the approval of Hong Kong Polytechnic University Ethics Committee.

The sample size calculation is based the significant findings of the gait speed and cortical silent period reported by Yang et al. (23). A two-way repeated measures ANOVA design with between-subject group effect (3 levels) and within-subject time effect (4 levels) determines that fifteen subjects per group are required to achieve 85% power to test the interaction effect between group and time effect with a 5% significance level and the effect size is 0.4. By assuming 10% dropout rate, 17 subjects will be required per group.

Experimental protocol

Part I & II. Mapping study and reliability study

Measures of cortical excitability including resting motor threshold (RMT) and recruitment curves will be obtained with transcranial magnetic stimulation (TMS) for 10 healthy subjects for study part I to identify the optimal site for TMS stimulation of the tibialis anterior (TA) muscles.

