Measures of cortical excitability including resting motor threshold (RMT), recruitment curves, intracortical inhibition (SICI) will be obtained with transcranial magnetic stimulation (TMS) for intra-rater and test-retest reliability of all these measures will be established for Study Part II. TMS assessment will be repeated twice, at least 1.5 hour apart within the same session for each study participant to assess the intra-rater reliability. Study participants will be asked to returned 1 week after for TMS assessment to assess the test-retest reliability.

Part III. Interventions

All assessment and treatment will be carried out at the electrophysiology and Gait and balance laboratory. Participants will be randomised into three groups i.e. two experimental groups and a sham group. Participants in the experimental groups will received either 1 Hz or 25Hz real rTMS and control group will receive sham rTMS, followed by treadmill training for 16 sessions over 8 weeks.

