All statistical analyses were performed using SPSS version 20.0 software (SPSS Inc., Chicago, IL, USA). Kolmogorov-Smirnov tests will be used to check the normality of data. One-way analysis of variance (ANOVA), Mann-Whitney U tests, and Chi-square tests will be used to compare the dependent variables (demographic data, daily dosage of levodopa, and the number of correct calculated answers/ walking time) among the 1Hz, 25Hz and sham groups. Two-way repeated measures ANOVA will be used to analyze continuous data with measurement interval (baseline, post-treatment, 2-month and 6-month post-treatment) as within-factor and group (1Hz, 25Hz, sham) as between-factor. In the case of an interaction effect between group and time being found, one-way repeated measure ANOVA and *t*-tests with Bonferroni adjustment will be used to determine the real differences. A significance level of 0.05 was employed for analysis.

5. Project Significance and Value:

The progressive and disabling features of PD are the major burden to patients themselves, their families and society as a whole. One of the most disabling motor symptoms is gait difficulty and postural instability. Beneficial long-term effects of rTMS and treadmill training suggest that this intervention could slow down motor function deterioration and maintain gait and balance performance for a relatively long period of time. To be able to walk safely and effectively will promote independence, enhance quality of life, prevent falls and reduced institutionalisation for people with PD.

References:

1. Wu T, Chan P, Hallett M. Effective connectivity of neural network in automatic movements in

Parkinson's disease. *Neuroimage* 2010;49:2581-2587

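### No blocking, stratification or Hoehn & Yahr term is specified for 51 patients in three arms; the cost is some power and precision, not a biased test.

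*Combined protocol and SAP*

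**What the plan says.** All places are in section 4, Research Methodology.

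- **Allocation (Part III. Interventions):** "Participants will be randomised into three groups i.e. two experimental groups and a sham group". No ratio, sequence method, block structure, stratification factor or list holder is given there or elsewhere.
- **Eligibility (Participants, part III):** "Hoehn & Yahr Scale Stage II to III with stable medications usage".
- **Sample size (Participants):** "Fifty-one participants with PD will be recruited". The calculation asks for 15 per group, to reach 85% power for the group-by-time interaction at the 5% level with an effect size of 0.4, and then allows for loss: "By assuming 10% dropout rate, 17 subjects will be required per group". Equal allocation is implied by this figure but not stated.
- **Baseline data (Data Collection):** age, gender, disease duration and medication are given as examples of what is recorded. Hoehn & Yahr stage is not among them.
- **Analysis (Statistical analysis):** a two-way repeated measures ANOVA with four time levels, baseline being the first, and "group (1Hz, 25Hz, sham) as between-factor". No covariate is named. Demographics and levodopa dose are compared between groups by significance tests. If the interaction is found, one-way repeated measures ANOVA and Bonferroni-adjusted t-tests follow.

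**The concern.** With about 17 patients per arm, chance can produce unequal arms and an uneven mix of stages. Stage is known before allocation, because it is an entry criterion, so balancing it costs almost nothing. As written, the plan neither balances stage by design nor includes it in the model. The baseline significance tests do not fill the gap: they may flag an imbalance but change nothing in the outcome analysis, and stage is not listed among the variables recorded.

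Objective 1 compares 25 Hz with 1 Hz on gait, over the short and long term. If stage II and stage III patients respond differently to training, or decline at different rates up to 6 months after treatment, that difference adds noise to the comparison. A visible stage imbalance would also make the result of this one trial harder to interpret.

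**Working it through.** **1. The plan's own figures.** Dropout: 15 / (1 − 0.10) = 16.7, rounded up to 17; 17 × 3 = 51. This reproduces exactly. Power: take the effect size of 0.4 as Cohen's f, with k = 3 groups, m = 4 times and N = 45. Use λ = (N − k)(m − 1)f²ε with degrees of freedom 6ε and 126ε. At ε = 0.75, λ = 42 × 3 × 0.16 × 0.75 = 15.12 and power is 0.861, so 15 per group meets 85%. The protocol states neither ε nor the type of effect size; both are assumptions here, and other standard variants give different group sizes.

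**2. Arm sizes, if simple 1:1:1 randomisation is used (assumption).** Arm sizes are multinomial(51; 1/3, 1/3, 1/3).

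- P(17/17/17) = 51! / (17!)³ / 3⁵¹ = 1.6%.
- P(smallest arm below 15, before any dropout) = about 65%.
- Mean increase in the variance of a pairwise comparison, against 17 v 17: about 4% (95th percentile 27%).

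**3. Stage mix with exactly 17 per arm and no stratification.** The stage III count in each arm is binomial(17, p). The protocol does not give p. A gap of 4 patients is 4/17 = 23.5 percentage points.

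| Assumed stage III share | Some pair differs by ≥ 4 | 25 Hz v 1 Hz differ by ≥ 4 |
|---|---|---|
| 30% | 38.6% | 19% |
| 40% | 44% | 22% |
| 50% | 45% | 23% |

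At a 20% share the first figure is 28%. At a 50% share, a three-arm chi-square test at 0.05 would flag only about 12% of these imbalances.

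**4. What such a gap does to an estimate.** Suppose stage III patients change by 0.5 SD more or less than stage II patients (assumption). A 4-patient gap shifts the between-arm difference in change by 4/17 × 0.5 = 0.12 SD. The standard error for 17 v 17 is √(2/17) = 0.34 SD, so the shift is about a third of one standard error. For stage effects of 0.3 to 0.8 SD it is about 0.2 to 0.55 of a standard error.

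**5. Type I error.** With simple randomisation and stage affecting both level and change, the simulated rejection rate for change from baseline under no treatment effect was 0.048, against a nominal 0.05.

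**6. Power.** This is a simplified simulation on a single change score. Assumptions: 51 patients, a 40% stage III share, and a stage effect on change of 0.3 to 0.8 SD. Stage-stratified blocks plus a stage term gained about 2 to 6 points of power over unadjusted simple randomisation, for example 0.86 to 0.89 at 0.5 SD. If stage has no effect, the stage term costs at most about 1 point.

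**7. What stratified blocks of 3 and 6 achieve.** The stage III difference between arms is 0 or 1 patient in about 89% of simulated allocations and never more than 2. The smallest arm was never below 15 before dropout.

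**The case against.** The strongest reply is that randomisation inference already allows for chance imbalance. This is correct: unequal arms and uneven stage mix do not bias the comparison, and type I error stays nominal. A typical imbalance also moves an estimate by only a fraction of its standard error (step 4).

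Four stronger readings are tempting, and the documents do not support them.

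- *A reader might infer that the trial is unblocked and unconcealed.* The protocol is silent on both; it does not say that they are absent. The requirement of 17 per group suggests that equal arms are intended. The figures in step 2 therefore depend on simple randomisation being used.
- *A reader might infer that nothing in the analysis deals with stage.* Baseline is one of the four time levels and the powered test is the group-by-time interaction, so a constant stage effect on the outcome cancels there. What remains is a stage effect on change, and level differences if the follow-up t-tests compare groups at single visits; the plan does not say which t-tests are meant.
- *A reader might infer that blocking would secure 15 completers per arm.* It would not. With exactly 17/17/17 and random 10% dropout, some arm still falls below 15 completers in about 56% of trials, against 92% under simple randomisation.
- *A reader might infer that undescribed concealment adds to the chance imbalance.* Concealment guards against selection bias, which is a different problem. The double-blind label and the blinded assessor do not describe it, but nothing shows that it is lacking.

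It is also fair to say that the documents give neither a stage mix nor evidence that stage modifies response, so choosing stage as the stratifier is partly a matter of judgement. It is a reasonable choice because it is already established at entry.

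**Conclusion.** The point holds as a gap in design and model efficiency. The plan specifies no blocking or stratification for 51 patients in three arms, and no stage term in the analysis. Material chance imbalance is then likely: about 65% for a smallest arm below 15 if allocation is simple, and about 39% to 45% for a gap of at least 4 stage III patients between some pair of arms even at 17 each, with a stage III share of 30% to 50%.

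The consequence is moderate: about 2 to 6 points of power under an assumed stage effect on change of 0.3 to 0.8 SD, little or nothing from the stage mix if stage does not affect change, and possible level differences in single-visit t-tests. The trial's validity is not in question on this ground. The change is worth making because it is cheap. The missing description of concealment is a reporting gap to close alongside it.

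**What to change.** **Part III. Interventions.** State 1:1:1 allocation from a computer-generated list in permuted blocks of randomly varying size 3 and 6, stratified by Hoehn & Yahr stage (II or III). Add stage to the variables recorded at baseline under Data Collection.

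**Statistical analysis.** Include stage and stage-by-time in the outcome model. A stage main effect alone adjusts only the level, which the interaction test already removes; stage-by-time is needed to adjust change.

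**Separately,** state who holds the concealed list (someone not involved in recruitment, treatment or assessment) and that each assignment is released only after the baseline assessment. This addresses selection bias.

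**Cost.** A few sentences and two lists to manage instead of one. Arm sizes may end a patient or two off 17. The model spends 1 degree of freedom on stage and 3 on stage-by-time (four visits minus one), with up to about 1 point of power lost if stage has no effect. The total stays at 51, with no added visits.

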than this, the principal of activity dependent neuroplasticity suggests that motor learning has to be task specific (22). Therefore, application of rTMS before specific motor training may boost up the training effect. Yang et al (23) recently demonstrated that 12 sessions over 4 weeks of 5Hz rTMS and treadmill training compared with treadmill alone led to better improvement of walking and functional mobility performance accompanied with some positive changes in intracortical inhibition. This modulation of intracortical inhibition has also been shown after high intensity treadmill training (24). These findings are very intriguing but further randomised control trials with more sample sizes are warranted to minimise bias. In addition, it is uncertain if the rTMS stimulation protocol used in Yang et al study is optimal. The carry over effect has also not been examined.

Therefore, this research projects aim to determine a rTMS stimulation protocol that would optimise the beneficial effect of treadmill training in PD by comparing the 2 different stimulation frequency protocols i.e. 1Hz and 25 Hz. In addition, rTMS has been found to restore the intracortical inhibition in PD (23). The restoration of the cortical inhibition through rTMS may have therapeutic effect on the defective cortical-basal ganglia-cortical network in PD (8). The inhibitory signals are essential for optimal execution of motor program by inhibiting other inappropriate and competing circuits. As discussed earlier, the basal ganglia allow well-learned movement such as walking to be performed with less attention resources. Hence, it would be interesting to investigate if rTMS would enhance the automaticity of walking and thus better dual-task walking performance.

Last but not least, it will be interesting to investigate whether combined rTMS and treadmill training can be transferred to enhancement of balance performance in PD as treadmill training has been found to reduce fall rate in PD (33).

4. Research Methodology:

Study Design: A double-blinded randomised controlled trial

Participants

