Magstim_200 magnetic stimulator (Magstim Company, Whitland, UK) and 90-mm double cone coil will be used to deliver TMS in this study. Each participant will be seated comfortably in a recumbent chair with arm and head supported by pillow. Small surface electromyography EMG electrodes will be attached to the belly of the TA with a ground electrode placed on the ankle. The motor evoked potential (MEP) in the TA will be recorded with surface EMG, which will be amplified with the band pass filtered between 10 and 1000Hz(Viking II Electromyography). All EMG traces will be stored for offline analysis.

Skin preparation using "3M One Step" skin prep abrasive sandpaper to reduce skin impedance will

be performed prior to the placement of the surface electrodes as well as the ground electrodes.

Resting Motor Threshold

Resting motor threshold of each participant will be determined with the following procedure: A latex swim cap will be placed on each participant's head and measurement of the vertex (Cz) will be marked on the cap. Subjects will be instructed to relax but to keep their eyes open during the whole procedure.

The coil is held centred over Cz, with a common longitudinal part of the coil along the interhemispheric fissure. Single TMS pulse will be delivered over the scalp overlying contralateral primary motor cortex that controls the TA. The MEPs of the bilateral tibialis anterior muscles will be recorded in response to TMS delivered with different coil orientation and location to determine the best coil orientation and hot spot. The site that evokes the largest and most consistent MEP amplitudes will be considered as the motor hot spot. The best coil orientation that evokes the largest and most consistent amplitudes will be adopted for subsequent TMS procedure of this study. This location with reference to Cz will be marked on the swim cap fitted for each subject. With the stimulus coil placed over the hot spot, stimulus intensity will be lowered gradually in a step-wise manner to determine the resting motor threshold (RMT). RMT is defined by minimal intensity that produces a MEP of a minimum of 50 μ V in 5 out of 10 consecutive trials.

Cortical silent period

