Repetitive transcranial magnetic stimulation. Repetitive TMS will be delivered to the scalp over the leg area of the motor cortex contralateral to the more affected side by using a Magstim200 magnetic stimulator (Magstim Company, Whitland, UK) and 90mm double cone coil in this study. Each participant will be seated comfortably in a recumbent chair with legs and head supported by pillow. The experimental group will receive either a 1Hz or 25 Hz of real rTMS with an intensity of 80% resting MT, a total of 1200 rTMS pulses to both hemispheres. For 1Hz rTMS, subjects will receive 3 trains of 200s-1Hz with 10 seconds inter train intervals to each hemisphere in 20 minutes. For 25Hz rTMS, subjects will receive 3 blocks (2 minutes break) of 8 trains of 1s-25Hz with 10s inter train intervals to each hemisphere in 20 minutes. The coil is centred over vertex and laterally offset to the leg area at the optimal site for response from the contralateral tibialis anterior (TA) muscle. A latex swim cap will be placed on each participant's head and measurement of the vertex will be marked on the cap. Subjects will be instructed to relax but to keep their eyes open during the whole procedure. The location of the stimulation will be marked, referenced by vertex-centred coordinates and recorded to maintain consistency among sessions. The sham rTMS will be delivered in the same setup and parameters of that of 25 Hz rTMS, however, with the cables of the coil disconnected. Another figure-of-eight coil delivering 25 Hz of rTMS will be placed posterior to the subject's neck. Subjects in the placebo group will be told that the stimulation intensity is sub threshold for muscle contraction.

Treadmill training. All participants will walk on a motorized treadmill after rTMS for 30 minutes. The

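### The protocol assigns the sub-threshold message to the sham group alone, although it fits both real-stimulation groups too, so participants receive different information by arm

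*Combined protocol and SAP*

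**What the plan says.** Section 4 describes the study as "A double-blinded randomised controlled trial". Part III randomises participants to 1 Hz rTMS, 25 Hz rTMS or sham, each followed by treadmill training.

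The paragraph on repetitive transcranial magnetic stimulation sets the intensity for the two real groups: "The experimental group will receive either a 1Hz or 25 Hz of real rTMS with an intensity of 80% resting MT". For the control group it says: "The sham rTMS will be delivered in the same setup and parameters of that of 25 Hz rTMS", but with the coil's cables unplugged. It adds a second device: "Another figure-of-eight coil delivering 25 Hz of rTMS will be placed posterior to the" participant's neck. It then closes with what this group is to hear: "Subjects in the placebo group will be told that the stimulation intensity is sub threshold for muscle contraction".

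The same paragraph gives a general instruction that names no arm: "Subjects will be instructed to relax but to keep their eyes open during the whole procedure". That instruction does not mention threshold.

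Under Data Collection, the outcome assessor is to be unaware of the group. How participants are kept unaware is not spelled out beyond the double-blinded label and the sham procedure.

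**The concern.** In a sham-controlled trial, what participants are told about their treatment should not depend on the arm. Here a statement about stimulation strength is prescribed for one arm by name, and nothing in the documents explains why it should be confined to that arm.

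The outcomes make this worth correcting. Comfortable and fast walking speed, timed up and go, their dual-task versions and the balance test all depend partly on effort and expectation. Treadmill training speed also follows what the participant tolerates and can maintain, so expectation could act on the training as well as on the test. If the groups are told different things, a difference between real and sham stimulation may contain a part due to the information and not to the stimulation. The planned analysis cannot separate the two.

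**Working it through.** The protocol gives no figure on this point to reproduce. The check sets its statements side by side.

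**Step 1. Are the real arms below threshold?** The Resting Motor Threshold section says "RMT is defined by minimal intensity that produces a MEP of a minimum of 50" microvolts in 5 of 10 consecutive trials. Intensity in both real arms is 80% of that threshold. Since 80% is less than 100%, both are sub-threshold by the protocol's own definition.

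**Step 2. Who is told what?**

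| Arm | Stimulation described | Sub-threshold message prescribed? |
|---|---|---|
| 1 Hz | Real, 80% of resting motor threshold | No statement found |
| 25 Hz | Real, 80% of resting motor threshold | No statement found |
| Sham | 25 Hz set-up, main coil unplugged, second coil at the neck | Yes, by name |

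**Step 3. Is the restriction just loose wording?** The instruction to relax with eyes open is addressed to subjects in general. The threshold message is addressed to the placebo group. The paragraph therefore distinguishes instructions for everyone from instructions for one arm, and staff who follow it exactly would give the message to sham participants only.

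**Step 4. Does the message give allocation away?** No. It describes the real arms just as well, so a participant who hears it, or an assessor to whom it is repeated, learns the arm only by also knowing that the other arms were not told.

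**Step 5. Which way could it act?** The baseline assessment takes place in the week before treatment and includes TMS well above threshold: 120% of resting motor threshold for the test pulse in paired-pulse testing, 130% for the cortical silent period and up to 180% on the recruitment curve. Participants in any arm may then notice that treatment feels weaker. Two readings are open:
- The message lowers sham participants' expectation by telling them that the stimulation is weak.
- The message reassures sham participants that quiet stimulation is normal, while real-arm participants, given no explanation, begin to doubt theirs.

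The documents do not decide between these.

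**Step 6. Which comparisons are exposed?** Those of 1 Hz with sham and of 25 Hz with sham, and through them the three-group interaction test. Neither real arm is prescribed the message, so the direct comparison of 25 Hz with 1 Hz, which is the subject of objectives 1 and 2, is not affected by it.

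**The case against.** The strongest reply is that the sentence ends the description of the sham and explains how it is made credible. It does not say that the real arms are not told. What every participant hears would normally be in the information sheet and consent form, and those pages are absent from the public text. This stands as a limit: a common script may exist, and then only the protocol sentence needs to be brought into line.

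It can also be said that resting motor threshold is an electromyographic threshold, not one for visible contraction, so sub-threshold in one sense need not mean sub-threshold in the other. The documents do not equate the two, but neither do they suggest that 80% of resting motor threshold would produce a contraction.

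A third reply is that larger masking differences remain: the neck coil is described for sham only, and 1 Hz and 25 Hz trains follow different patterns. That is true, and a common script removes neither. It limits the benefit of the change but is no reason to keep an avoidable difference.

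A reader might go further than the documents allow in three ways:
- **That the message unblinds participants or the assessor.** It does not on its own, because it is equally apt for the real arms.
- **That the bias favours real stimulation.** Either direction is plausible, and the text settles neither.
- **That a false-positive rate can be attached.** This would need an assumed expectation effect, for which the documents give no basis. A simple two-group t-test would also not represent the plan, which tests a group-by-time interaction first and makes Bonferroni-adjusted comparisons only if that is found.

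**Conclusion.** The point holds as a matter of wording. The protocol prescribes a message for the sham group only, the message suits the two real groups equally well, and the trial is described as double-blinded. Exact compliance gives participants different information by arm.

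The size and direction of any resulting bias in the gait and balance outcomes cannot be derived from the documents, and no figure is offered. Exposure is confined to the contrasts with sham.

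The conclusion rests on two assumptions: that staff follow the protocol as written, and that no common script in the participant materials already overrides the sentence. This is a free improvement, not evidence that blinding will fail.

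**What to change.** Replace the sentence addressed to the placebo group with one that covers everyone, for example:

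> Participants in all three groups will be told, in the same words and at the same point, that stimulation is given at an intensity below the threshold for muscle contraction.

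Check that the consent form and the script used by treatment staff carry the same statement. If a common script already exists, the protocol should refer to it.

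The cost is one protocol sentence and a check of the participant materials. Stimulation settings, visits, staffing and sample size are unchanged.

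### The rank test named for the three-arm comparisons, Mann-Whitney U, handles only two groups; Kruskal-Wallis should be named instead (minor, secondary variables only)

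*Combined protocol and SAP*

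**What the plan says.** Part III has three arms: "Participants will be randomised into three groups i.e. two experimental groups and a sham group". The Statistical analysis text begins with a Kolmogorov-Smirnov check of normality and then states: "One-way analysis of variance (ANOVA), Mann-Whitney U tests, and Chi-square tests will be used to compare the dependent variables". The variables are listed as "demographic data, daily dosage of levodopa, and the number of correct calculated answers/ walking time", and the comparison is made "among the 1Hz, 25Hz and sham groups".

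Continuous data then go to a two-way repeated measures ANOVA with three groups and four time points. If a group-by-time interaction is found, one-way repeated measures ANOVA and t-tests "with Bonferroni adjustment will be used to determine the real differences". That is the only multiplicity adjustment in the document. The level is given once, for everything: "A significance level of 0.05 was employed for analysis".

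**The concern.** Because the sentence follows a normality check, Mann-Whitney U reads as the route for variables that fail it. It is the only one of the three named tests that cannot compare three groups at once. It can be applied only to pairs of arms, and three arms make three pairs. The plan does not say whether one, two or all three pairs would be tested, and the Bonferroni step belongs to a different analysis.

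Two things are at stake. The choice of pairs stays open until the data are seen. And if all pairs are tested and any p-value below 0.05 is read as a difference among the arms, the error rate per variable exceeds the stated level. A spurious difference in levodopa dose or in counting performance could then colour how the gait results are read. For example, faster dual-task walking might be put down to a trade-off with the counting task.

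**Working it through.** **Inputs from the document**
- Three arms, so 3 × 2 / 2 = 3 pairs (Part III. Interventions).
- Level 0.05 (Statistical analysis). Sidedness is not stated; two-sided is assumed.
- Evaluable size: "fifteen subjects per group are required to achieve 85% power to test the interaction effect between group and time effect". Enrolled size: "By assuming 10% dropout rate, 17 subjects will be required per group".

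**The plan's own figures.** 15 / (1 − 0.10) = 16.7, rounded up to 17 per arm, and 3 × 17 = 51, as stated. The document gives no overall error rate for the rank comparisons, so there is no figure of that kind to reproduce.

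**Chance of at least one p < 0.05 across three unadjusted pairs, with no true difference**

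1. Upper guide, treating the pairs as independent: 1 − 0.95³ = 14.3%. This is too high, because each arm appears in two of the pairs.
2. Large-sample value that allows for the shared arms: the probability that the range of three independent standard normals exceeds 1.96 × √2 = 2.77. The studentized range distribution (3 groups, infinite degrees of freedom) gives 12.2%.
3. Simulation at the planned sizes (200,000 trials per size, continuous data without ties):

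| Procedure | 15 per arm | 17 per arm |
|---|---|---|
| Any of three pairs, 0.05 each, exact p-values | 11.1% | 11.9% |
| Any of three pairs, 0.05 each, normal approximation | 12.2% | 11.9% |
| One single pair, 0.05, exact | 4.4% | 4.8% |
| Any of three pairs, 0.05/3 each, exact | 4.3% | 4.2% |
| Kruskal-Wallis, 0.05 | 4.7% | 4.7% |
| One-way ANOVA, 0.05 | 5.0% | 4.9% |

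Each Mann-Whitney test keeps its own level. The excess comes from reading three of them as one three-arm comparison.

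**Kruskal-Wallis first, then Mann-Whitney at 0.05.** If no arm differs, a pairwise claim needs a significant Kruskal-Wallis result first, so the rate cannot exceed that test's level. If one arm differs from the other two, only one pair has no true difference, and that pair is tested at 0.05. Simulation gave 4.6–4.8% with no difference and 4.1–5.0% when one arm differed. Adding the 0.0167 threshold after the gate would cut the power for a given pair from about 66% to about 54%, for one arm shifted by 1 SD with 15 per arm.

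**The case against.** The strongest reply is that the 11–12% describes one reading of an ambiguous sentence. The plan never says that all three pairs will be run, nor that one significant pair will be reported as a three-arm difference. It sets one significance level, and each Mann-Whitney test respects it. This stands, so the figure has to stay conditional.

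A reader might also infer that the stated methods cannot answer the three-arm question at all. That goes too far: ANOVA and chi-square in the same sentence can. Only variables unsuited to both would reach Mann-Whitney, and the document does not say which those are.

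Nor does the weight of the affected variables support a stronger charge. At baseline, differences between randomised arms in demographics or dose are chance, and the plan attaches no covariate choice or adjusted analysis to a significant result. The dual-task answer score is closer to an outcome, since dual-task gait is part of objective 1. But it is not listed under Outcome measures, its visit is not specified, and as a rate it could equally fall under the repeated measures ANOVA of continuous data. Levodopa dose is recorded at every assessment, but again the tested visit is not named.

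What the reply does not remove is the mismatch itself: a two-group test is named for a three-group comparison, and no three-group rank test is given.

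**Conclusion.** The point holds as a minor correction. The named rank test does not fit the stated comparison, and nothing elsewhere in the plan repairs it. Its size, about 11–12% per variable instead of 5%, rests on four assumptions: all three pairs are run, no adjustment is made, the tests are two-sided, and there are 15 to 17 per arm without heavy ties. Ties or unequal dropout would move it slightly.

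A reader might infer that the trial's main conclusions carry an inflated error rate. The document does not support that. Gait speed and the cortical measures are continuous and go to the two-way repeated measures ANOVA, which is also the analysis behind the sample size. The authors may have meant Kruskal-Wallis with Mann-Whitney follow-up all along; if so, the text only needs to say it.

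**What to change.** In the Statistical analysis text, replace the Mann-Whitney U tests with Kruskal-Wallis tests for the three-arm comparison of non-normal or ordinal variables. State that Mann-Whitney U is used only for pairwise follow-up when the Kruskal-Wallis result is significant at 0.05. It would help to say in the same line which visit the levodopa dose and the dual-task answer score are compared at, and whether that score belongs here or in the repeated measures ANOVA.

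The cost is a line or two of text, with no change to data collection, sample size or participant procedures. A further 0.05/3 = 0.0167 threshold for the pairwise tests may be added but is not needed with three arms, and it carries the loss of pairwise power shown above.
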